
Study Design

Methods

We will conduct a cluster randomized trial to examine the impact of NEST on the decision-making process about NIPT from the perspectives of pregnant women, partners, and providers. As outlined in the initial NIH proposal, our plan is to recruit from multiple healthcare systems. We will begin with Cleveland Clinic. Once we have established streamline recruitment and data collection procedures, we will then extend research activities to the MetroHealth System.

We will utilize the following measures: 1) with the patient's permission, direct observation of the first prenatal visit to measure the primary outcome and 2) a series of surveys to measure secondary outcomes in addition to gain information about the instrument usability and feasibility. The same measures will be used at MetroHealth as they are for the Cleveland Clinic.

PARTICIPANTS AND RECRUITMENT PROCEDURES

Study populations will include the following groups:

I: Pregnant women

II. Partners of pregnant women enrolled in the study

III. OB providers

I. Pregnant women

Study participants will include pregnant women who receive prenatal care at one of the prenatal care outpatient clinics of Cleveland Clinic or MetroHealth. We will utilize the same inclusion and exclusion criteria for the Cleveland Clinic and MetroHealth.

Inclusion and exclusion criteria for this group are as follows:

Inclusion criteria:

- 1) 18 years of age or older
- 2) Present for their initial prenatal visit care with one of the providers enrolled in the study
- 3) Able to provide consent to participate in the study
- 4) Available for follow-up survey completion in the 1st and 2nd trimester of pregnancy
- 5) Have a viable intrauterine pregnancy
- 6) Present for care between 7–12 weeks estimated gestation age (EGA)
- 7) Ability to read and speak English

Since criteria 5 and 6 will not be determined until the conclusion of the first prenatal visit, women who meet criteria 1–4 will be eligible for participation.

Exclusion criteria:

Women who are:

- 1) Less than 18 years of age
- 2) Not currently pregnant or an intrauterine pregnancy has not yet been established
- 3) Inability to provide informed consent for research participation
- 4) Inability to speak or read English

Recruitment Procedures:

A. Cleveland Clinic

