The research coordinator will obtain the providers' written informed consent for the study participation; a fully signed copy will be provided to the provider and another copy will be kept on file in a locked cabinet in [name] office at MetroHealth.

Following recruitment and informed consent procedures, OB providers will be randomized by practice into one of two study arms: (1) the intervention arm utilizing NEST or (2) the control arm utilizing standard practice patterns for education and counseling (usual care). Randomization by practice will prevent contamination between study arms, as a patient may see more than one provider within a practice over the course of her pregnancy. A cluster will be an outpatient clinic and contain the providers who practice at that location. The intervention will be delivered to the cluster as a whole. Thus, all participating providers within a cluster will be randomized to the same arm. Practices within the healthcare system will be stratified by both practice and patient-population characteristics. A binary random number generator will be used to assign NEST or control status at the practice level. The assignment will be checked to ensure a balance with respect to the number of clusters and providers in each of the study arms. Imbalances will be corrected manually, and the resultant groupings will be checked to ensure that randomization has been preserved. Participating providers in practices randomized to the intervention arm will receive a training session to orient them to NEST prior to data collection activities. Because NEST is targeted to affect the patient-provider interaction, study participants will not be blinded to which group they have been allocated.

All participating providers at Cleveland Clinic and MetroHealth will be asked to review the most current clinical practice guidelines as developed by the American College of Obstetricians and Gynecologists (ACOG) and Society for Maternal Fetal Medicine (SMFM). These guidelines will be emailed to each provider once their first patient has expressed interest in participating.

We will return to previous methods of enrolling providers into the NEST study at both MH and CCF.

DATA COLLECTION INSTRUMENTS AND PROCEDURES

We will utilize the same data collection instruments at both the Cleveland Clinic and at MetroHealth.

I. Pregnant participants

Data collection instruments and intervention:

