Data from the surveys will be collected either 1) using a tablet PC enabled with REDCap Survey for direct data entry or, if necessary, due to technical issues 2) on paper surveys with manual entry by the research team into REDCap. This is only done if there is a technical issue with the iPads or printers (internet connectivity problems, battery issues, etc.).

The following analysis will be conducted with the Principal Investigator in conjunction with [name], the QHS statistician designated to the WHI using JMP and SAS:

Data from the direct observation will be analyzed using the *observed* OPTIONS scale. This is a validated scale similar to the *dyadic* OPTIONS scale but developed for direct observation measurement of SDM in the clinical encounter. The *observed* OPTIONS scale will be utilized in conjunction with a content checklist to determine if the information exchanged during discussions of prenatal genetic risk and assessment meets the needs and preferences of patients, the recommendations of OB providers and GCs published by the American College of Obstetricians and Gynecologists, and clinical practice guidelines. The checklist was developed using data from our preliminary studies.

Audio recordings from the direct observation will be transcribed verbatim for analysis. Transcriptions will be coded by two independent coders using the *observed* OPTIONS scale and content checklist. Measures will be analyzed as a function of exposure (NEST vs. control) and visit composition (patient only vs. patient/partner pairs). The content checklist will be utilized to assess discussion content and to determine fidelity to the intervention. Transcriptions will be time-stamped to determine the length of discussions pertaining to prenatal genetic risk and assessment in NEST vs. control groups. Tukey-Kramer comparisons will be made to adjust for multiple comparisons. The matrix of predictor variables of intervention, patient characteristics, including variables of baseline knowledge and attitudes, presence of partner at the visit, and provider characteristics will be examined using the co-linearity tests of variance inflation factors and condition indices. Those variables exhibiting sufficient independence will be included in the multivariable analysis. Kappa statistics will be calculated to assess the degree of agreement between the coders; a third coder will be brought in if consensus cannot be reached.

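### Practices are stratified within health system before randomisation, but no NEST-versus-control analysis carries a health-system or stratum term; it should be added together with a practice-level term

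*Combined protocol and SAP*

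**What the plan says.** The randomisation text, under OB providers in the recruitment section, defines the unit: "A cluster will be an outpatient clinic and contain the providers who practice at that location". It then states: "Practices within the healthcare system will be stratified by both practice and patient-population characteristics". Arms are allocated as follows: "A binary random number generator will be used to assign NEST or control status at the practice level". No block size or within-stratum ratio is given. The check afterwards is on totals: "The assignment will be checked to ensure a balance with respect to the number of clusters and providers in each of the study arms". Then: "Imbalances will be corrected manually, and the resultant groupings will be checked to ensure that randomization has been preserved". The strata themselves are not listed.

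Study Design, Methods, says that "our plan is to recruit from multiple healthcare systems". Two are named, and they start at different times: "Once we have established streamline recruitment and data collection procedures, we will then extend research activities to the MetroHealth System".

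For the audio-recorded visit, which carries the primary outcome, the Data Analysis section states: "Measures will be analyzed as a function of exposure (NEST vs. control) and visit composition (patient only vs. patient/partner pairs". A multivariable analysis follows. Its candidates are the intervention, unlisted patient characteristics, whether a partner attended, and unlisted provider characteristics, each kept only if it passes a collinearity screen. A further paragraph analyses results by intervention alone. Health system, site, practice and stratum appear in none of these.

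**The concern.** Factors judged important enough to stratify on normally belong in the model, and here the outermost one, health system, is missing. MetroHealth starts later, words its MyChart invitation differently, schedules through different staff, and enrols in person or electronically while Cleveland Clinic is restricted to electronic outreach and consent. These differences can change who enters the recorded sample, and the two systems may also counsel differently. The documents do not say how far the scores differ.

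If they do differ, what is at stake depends on the realised allocation. With the systems evenly split, the difference between them stays in the error of a practice-level comparison and costs power. With an uneven split, part of that difference is attributed to NEST. The balance check would not reveal this, because two arms can hold equal numbers of clusters and providers and still contain different mixes of the two systems.

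**Working it through.** **Inputs.** The main trial states no sample size, power, alpha, number of practices, ICC or score SD; the only target is 40 interviews in the sub-study. There is therefore no plan figure to reproduce. Assumed for illustration:
- 16 practices, 4 of them MetroHealth (share p = 0.25)
- m = 15 recorded visits per practice
- ICC 0.05
- two-sided alpha 0.05
- an effect sized for 80% power with the health-system term
- a health-system difference D of 0.3 to 0.5 within-system SD

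**(a) Systems evenly split, practice-level analysis.**
- Variance of a practice mean: v = ICC + (1 − ICC)/m = 0.05 + 0.95/15 = 0.1133.
- Variance added by omitting the term: p(1 − p)D² = 0.1875D², which is 0.0169 at D = 0.3 and 0.0469 at D = 0.5.
- Inflation of the standard error: r = √(1 + 0.1875D²/v), which is 1.072 and 1.189.
- Normal approximation: power = Φ(1.96 + 0.84 − 1.96r), which is 76% and 68%.
- Simulated t-tests on practice means (14 degrees of freedom without the term, 13 with it) give about 75% and 65% to 67% across runs, against 80% with the term.
- Over 12 to 16 practices and ICC 0.01 to 0.10, the simulated loss is about 3 to 8 points at 0.3 SD and 9 to 25 points at 0.5 SD.
- At D = 0.2 the approximation gives r = 1.033 and power 78%.

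**Same case, encounter-level analysis.**
- Inflation is r = √(1 + 0.1875D²), which is 1.008 and 1.023. Power is 79.5% and 78.7%, a loss of about 0.5 to 1.3 points.
- This test ignores clustering. The design effect is 1 + 14 × 0.05 = 1.7, so the false-positive rate is 2[1 − Φ(1.96r/√1.7)], about 13% at 0.3 SD and 12% at 0.5 SD.
- With the health-system term but still no practice term, r = 1 and the rate is about 13%.

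**(b) Systems unevenly split.**
- With 8 practices per arm and MetroHealth split 3:1, the gap in MetroHealth share is 3/8 − 1/8 = 0.25.
- The shift is 0.25 × D: 0.075 SD at D = 0.3 and 0.125 SD at D = 0.5.
- If only the 8:8 total is guaranteed, P(2:2) = C(4,2)·C(12,6)/C(16,8) = 5,544/12,870 = 0.43. A split other than 2:2 then has probability 57%.

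**Cost of the term if D = 0.** In the same simulation, power with the term is under 1 point lower when the systems are evenly split. It is a little over 3 points lower (about 81% to 77%) when only the totals are balanced.

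**The case against.** **Covariates may stand in for strata.** The multivariable analysis is open-ended, and its patient and provider characteristics could overlap with the stratifying factors. This is partly right. But the covariates are unlisted, are not tied to the strata, and may be screened out; health system is not obviously either kind of variable.

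**The systems may hardly differ.** Both use the same eligibility criteria, measures and instruments, and all providers are asked to review the same guidelines. This stands as a limit on size: nothing in the documents supports a particular difference.

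**Stratification may already balance the systems.** If allocation was blocked within each system, the split is even, (b) disappears and only (a) remains. The text states no blocking, so the 57% shows what the stated check permits and is not a forecast.

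**Stronger readings a reader might infer, which the documents do not support:**
- *The planned test is too conservative.* That holds for a practice-level test with evenly split systems, which the plan does not describe. Read at encounter level with ICC 0.05, the test is anti-conservative.
- *The plan both loses much power and has an inflated false-positive rate because the stratum is missing.* No single analysis shows both. The large power loss needs a practice-level test. An encounter-level rate of 9% to 16% arises only given a 3:1 split and zero within-system ICC. A practice-level test averaged over allocations balanced only in total stays at about 5%.
- *The NEST estimate is biased.* The shift belongs to one allocation and is symmetric over repeated random allocation, although manual correction weakens that protection.
- *A stratum term repairs the analysis.* Without a practice term, the encounter-level error stays near 13%.

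**Conclusion.** The gap is real: the design stratifies within health system, and no stated comparison of the arms adjusts for health system or stratum. The consequence is conditional on the systems differing in the outcome. If they do, a practice-level analysis with evenly split systems loses roughly 5 points of power at 0.3 SD and 13 to 15 points at 0.5 SD, and a 3:1 split moves the estimate by 0.075 to 0.125 SD. In an encounter-level analysis with an even split, the loss is about 1 point and the absence of a practice-level term is the dominant defect. Every size rests on assumed numbers of practices and visits, an assumed ICC and an assumed system difference. The change is worth making because it costs little, but it is only useful alongside a practice-level term.

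**What to change.** In the Data Analysis section, state that each NEST-versus-control comparison will be fitted with:
- a random effect for practice, or an analysis of practice-level summaries, with small-sample degrees of freedom;
- a fixed term for health system (Cleveland Clinic or MetroHealth), kept whatever the collinearity screen shows;
- the other stratifying factors used at randomisation only where the number of practices allows, with sparse strata merged by a rule set before analysis.

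The stratifying factors must first be listed, since the protocol does not name them. The NEST Intervention paragraph places randomisation at the level of the OB provider, while the randomisation text places it at the practice; these must be reconciled so that the random effect matches the unit randomised.

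The cost is wording plus one or a few practice-level degrees of freedom. For the health-system term alone this is about 1 to 3 power points if the systems do not differ, and more if many strata are added, which is why the remaining factors are conditional. Sample size and procedures do not change.

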Per the original protocol, a database will be constructed using the EMR which will include patients' contact information, including MRN, DOB, mailing address, email address and telephone number(s), name of provider and date and place of upcoming prenatal appointment as described in the initial protocol. Initially, recruitment of patients was to take place by mailing a recruitment letter to eligible patients who are scheduled to see one of the providers at the recruitment sites for prenatal care. Given that the study entails identifying women's baseline

knowledge and health literacy with respect to genetics, heritable risk, and the fetal genetic risk assessment process at the first visit, the time to collect these data before the initial prenatal visit is limited. Contact for study recruitment needs to be made in the window before the initial prenatal visit where patients will discuss prenatal testing with their physician or midwife as part of the standard practice of obstetric care. This is a limited window as there is only a short interval of time between when a patient may schedule the initial prenatal visit (e.g., at 7-8 weeks EGA) and the time of her initial prenatal visit (e.g.; 9-10 weeks EGA). Because of this limited window, we therefore need a method of communication that allows for contact with patients who meet the study inclusion criteria in an expeditious manner.

Three options to contact the patients include use of 1) MyChart message, 2) EPIC NEST pool, 3) in person at the clinic visit and 4) Mailers

- 1) We will recruit participants using MyChart. We will recruit participants by sending an IRB-approved message via MyChart to eligible patients scheduled to see one of the study providers at the recruitment sites for prenatal care. The MyChart message will give a brief overview of the study, the benefits and risks, and give instructions to the patient to contact the Research Coordinator if interested in participation. The interested patient will be sent further information regarding the research study via email or postal mail, based on her preference.

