We will utilize a series of questionnaires to assess the study outcomes. This includes the questionnaires administered at different stages of pregnancy in addition to the intervention. These were developed by the following procedures:

[name] and her research team, with the input of the study Co-Investigators and members of the Advisory Panel, developed draft instruments based on existing validated instruments in the literature. Specific instruments include:

- (1) Multidimensional Measure of Informed Choice (MMIC), a validated tool that uses to multiple choice and Likert-scale items to measure knowledge, attitudes, and decision-making associated with prenatal genetic testing
- (2) Decisional Regret Scale (DSC), a validated scale using Likert-scale items to measure satisfaction/regret with the decision-making process (not the outcome of the decision).
- (3) Medical Term Recognition Test (METER), a validated tool used to assess health literacy. In METER, a list of 70 terms are given to a participant that contain some real medical words (i.e. words that have to do with body parts, body functions, types of diseases, etc.). The list also contains some items that may look or even sound like medical words but are not actually real words. The participant is given instructions to place an “X” next to the words they recognize to be real words. The participant is also told they should not guess and to only put an “X” next to a word if they are sure it is a real medical word.

Questionnaire development involved a process of modifying the MMIC. Because the MMIC developed several years ago, modifications were required to ensure that the instruments were able to assess primary and secondary outcomes. Initial survey items were developed through a consensus-building process among the study co-investigators. The instruments were then tested through a process of cognitive interviews (Amendment #1). The draft instrument was revised based on this process and then utilized for data collection. The finalized instruments were approved for use by the IRB (Amendment #5).

The data collection instruments are as follows:

- a. Baseline questionnaire (**QBASE**): This survey will collect the following information: (1) participant demographic and reproductive history information, (2) healthcare decision-making preferences, (3) participant knowledge and (4) familiarity with the concept of shared decision-making.

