- b. Post initial visit questionnaire (**QPV**): This survey will collect the following information: (1) participant knowledge, attitudes, and decision-making regarding NIPT (alternative tests or no testing), (2) health literacy.
- c. Time of testing questionnaire (**QTT**): This survey will collect the following information: (1) participant knowledge, attitudes, and decision-making regarding NIPT (alternative tests or no testing) and (2) decisional regret.
- d. Follow-up questionnaire (**QFF**) This survey will collect the following information: (1) participant knowledge, attitudes, and decision-making regarding NIPT (alternative tests or no testing) and (2) decision-making regret.

Measures	Baseline (QBase)	Post visit (QPV)	Time of test (QTT)	Follow up (QFF)
Demographics	X			
Shared decision-making and decision-making preferences	X	X	X	X
Informed choice/MMIC		X	X	X
Decisional regret/DSC			X	X

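### The multivariable model gives the NEST term no guaranteed place and no fixed covariates, and it names baseline attitudes that the surveys list only after the primary-outcome visit

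*Combined protocol and SAP*

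**What the plan says.** **The rule.** The candidates in the Data Analysis section begin "The matrix of predictor variables of intervention, patient characteristics, including variables of baseline knowledge and attitudes, presence of partner at the visit" and go on to provider characteristics. The whole set is examined with "co-linearity tests of variance inflation factors and condition indices". Then comes the entry rule: "Those variables exhibiting sufficient independence will be included in the multivariable analysis". There is no threshold, no rule for which of two collinear variables goes, no exemption for the intervention and no fixed covariate list. The same section separately says that measures are analysed by exposure and by visit composition. It labels neither analysis as primary.

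**Where the covariates come from.** Under the data collection instruments for pregnant participants, QBASE collects demographics and reproductive history, then "2) healthcare decision-making preferences, (3) participant knowledge and (4) familiarity with the concept of shared decision-making". Attitudes are not listed. QPV collects "1) participant knowledge, attitudes, and decision-making regarding NIPT (alternative tests or no testing), (2) health literacy" and is administered about 7-10 days after the first visit (7-9 days in the procedure lists at the end). The primary outcome, shared decision-making on the OPTION scale, comes from the audio recording of that first visit.

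**Randomization.** The section on OB providers says "Practices within the healthcare system will be stratified by both practice and patient-population characteristics". The Data Analysis section names neither these factors nor health system as model terms.

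**The concern.** A treatment effect should be estimated from a model in which the treatment term is present by design. Here it competes for entry on the same footing as the covariates. NEST is constant within a practice, so with few practices it can be correlated by chance with practice-level or provider-level variables and show a high VIF. Even if NEST is kept, the adjustment set, and with it the quantity estimated and its precision, depends on an undefined threshold applied after the data are in.

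The attitudes covariate is a different problem. If the only available attitude score is the one in QPV, it is measured after both the intervention and the outcome visit. NEST is meant to change how patients think about testing, so conditioning on that score could remove or distort part of the effect under study. In a complete-case analysis it would also lose recorded visits for which QPV was not returned.

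**Working it through.** The documents state no number of practices, sample size, effect size or correlation for the trial, so there is no figure to reproduce. The numbers below are illustrations under stated assumptions.

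**1. Bias from a covariate that NEST has shifted.** Let T be arm and U an unmeasured patient trait. The covariate is C = aT + ρU + noise and the outcome is Y = dT + bU + noise, with C and Y each of unit variance within arm. Regressing Y on T and C gives C the coefficient ρb and T the coefficient d - aρb. The bias is therefore -aρb. Assume ρ = 0.7:

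| Shift a (SD) | Slope b | Bias -aρb | A true 0.50 SD becomes |
|---|---|---|---|
| 0 | 0.3 or 0.5 | 0 | 0.50 |
| 0.2 | 0.3 | -0.042 | 0.458 |
| 0.2 | 0.5 | -0.070 | 0.430 |
| 0.5 | 0.3 | -0.105 | 0.395 |
| 0.5 | 0.5 | -0.175 | 0.325 |

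A simulation with 400,000 records agreed to within 0.01.

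**2. Whether the screen itself biases the estimate.** VIF and condition indices do not use the outcome. A simulation took 120 patients, no clustering, five covariates correlated 0.8, a true effect of zero, NEST always kept, and VIF cut-offs of 2.5, 5 and 10.

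- Covariates unaffected by arm: bias about 0, type I error 4.8-5.2%.
- All five covariates shifted by 0.5 SD: bias -0.12 to -0.16, rejection 9-13%.

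The bias comes from the shifted covariates. The cut-off only changes its amount.

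**3. The chance that NEST fails the screen.** VIF = 1/(1 - R²), where R² is from regressing arm on the other predictors. VIF above 2.5 means R² above 0.6; VIF above 5 means R² above 0.8. For K practices and p unrelated covariates that are constant within practice, R² follows Beta(p/2, (K - 1 - p)/2):

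| K | p | P(VIF > 2.5) | P(VIF > 5) |
|---|---|---|---|
| 10 | 3 | 11.7% | 1.6% |
| 10 | 5 | 44.2% | 14.1% |
| 14 | 5 | 13.0% | 1.1% |
| 20 | 5 | 1.5% | below 0.1% |

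Provider characteristics need not be constant within practice. A cluster contains the several providers at one clinic, and the OBP survey records each provider's own familiarity, confidence and opinions. With K = 10, p = 5 and 4 providers per practice, simulation gives P(VIF > 2.5) as follows:

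- about 0-2% at intra-practice correlation 0.1-0.5;
- about 15% at 0.8;
- 44% at 1.

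With 3 to 5 providers and correlation up to 0.5, the range is 0-4%, and VIF above 5 occurs in at most about 0.05% of trials.

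**The case against.** Several points on the other side are sound.

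- **The screen is blind to the outcome.** A reader might infer that it biases the effect or inflates type I error by itself. With true baseline covariates it does neither, as step 2 shows.
- **The 44% figure is an extreme.** It needs covariates that are constant within practice, together with an assumed number of practices, number of covariates and cut-off. It also ignores the stratification of practices. Nothing in the documents supports quoting it alone.
- **Attitudes in QBASE.** The questionnaire itself is not in the documents, and the measures table is incomplete: it has no separate knowledge row and omits health literacy. The analysis section calls the attitudes baseline. This is an inconsistency to reconcile, and it does not prove that QPV attitudes would be used.
- **Health literacy.** The Cleveland Clinic recruitment text speaks of baseline "knowledge and health literacy with respect to genetics, heritable risk, and the fetal genetic risk assessment process at the first visit", whereas the instrument list puts health literacy in QPV. But the Data Analysis section does not name it; it could enter only as an unspecified patient characteristic.
- **Partner presence.** It is recorded at the visit, and the NEST report may be shared with a partner. An effect of NEST on who attends is speculative, and visit composition is a stated factor of interest.
- **Strata.** The general terms for patient and provider characteristics may already cover some of the stratification factors.
- **Which analysis is affected.** A comparison by exposure without the screen is also planned, and the multivariable model is not called primary.

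What survives is the rule as written and the unexplained source of baseline attitudes.

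**Conclusion.** The point holds in this form. The stated rule gives NEST no guaranteed place in the multivariable model and leaves the covariate set open, and one named baseline covariate has no listed source before the outcome visit. Dropping NEST is probably not intended, but the text does not prevent it. Its probability depends on the number of practices and the within-practice variation of provider characteristics, neither of which is given.

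The bias of -0.04 to -0.18 SD applies only if QPV attitudes are used, if NEST shifts them by 0.2-0.5 SD, and if the assumed correlations are about right. With no shift there is no bias. The documents do not support a claim that the trial's primary result is already biased, or that the unscreened comparison by exposure is affected. The change is worth making because it costs almost nothing and the present rule has no compensating benefit.

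**What to change.** Replace the entry rule with a fixed multivariable model, written before the data are examined:

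- NEST is always kept.
- Health system and the stratification factors used at randomization are always included.
- Add a short named list of QBASE covariates: knowledge and decision-making preference.
- Use VIF and condition indices as diagnostics only, with no bearing on entry.
- State where baseline attitudes are measured. Keep attitudes and health literacy measured at QPV out of the adjusted model for the primary outcome.
- Report partner presence or visit composition as a secondary or sensitivity analysis.
- Require QBASE before NEST. Practices are allocated before patients enrol, both surveys are sent together in the intervention arm, and the Study Intervention text allows them to be completed at the same sitting without fixing the order. The MetroHealth virtual-visit instruction puts NEST first. Those visits are not recorded, so they do not supply the primary outcome, but the instruction should be brought into line.

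Moving the health literacy test or attitude items into QBASE is optional and would help only women not yet enrolled. The cost is a change of analysis wording, slightly less analyst flexibility and a fixed survey order.
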